7.2 Statistical and analysis plan

An intention to treat analysis will be conducted. All outcomes will be analyzed using generalized linear models (GLMs) and will include stratifying variables of BMI and clinic site as covariates. Primary outcome and all other binary outcomes will be analyzed with a logistic model. Secondary outcomes will be analyzed using appropriate distributional assumptions, i.e. negative binomial for counts and normal for continuous outcomes. We will report relative risks or group mean differences and 95% confidence intervals (CIs). Differences in costs will be assessed using a generalized linear model (GLM) with log-

link and gamma distribution. We will also compute the incremental cost-effectiveness ratio (ICER) of the total health system costs (savings) per prevented mother-infant dyad from developing an adverse outcome using a joint GLM with log link for costs and probit for maternal or neonatal adverse outcomes. We will induce dependency between costs and the adverse outcomes through shared random effects in the joint model.

Planned Bayesian analysis:

We will also conduct a Bayesian analysis of the primary outcome and of costs and cost-effectiveness. Sample size calculations using a Bayesian analysis with different probability thresholds are presented in Table 4. The composite primary outcome will be evaluated with a Bayesian binomial model. Finally, we conservatively set a neutral prior probability centered at a relative risk (RR) of 1.0 (*i.e.*, a priori no effect on the outcome) and a 95% credible interval of 0.3-3.3 encompassing the largest likely effect size for major outcomes in randomized trials. This neutral prior will also be used to assess cost differences between the two treatment groups. Finally, we will report RR and 95% credible intervals and the probability of reduced adverse neonatal outcomes and costs, as well as the probability that the ICER will fall in the dominant quadrant of the cost-effectiveness plane (Figure 1).

Table 4: Bayesian power to declare efficacy depending on level of evidence (probability threshold)

Control Rate	Treatment Rate	# patients /group	Prob(RR<1) > specified threshold					
			70%	75%	80%	85%	90%	95%
0.4	0.24	60	0.92	0.89	0.85	0.79	0.71	

	0.75	0.82	0.85	0.89	0.93	120	0.28	0.4
	0.90	0.93	0.96	0.98	0.98	110	0.24	0.4
	0.90	0.94	0.96	0.97	0.98	210	0.28	0.4
0.80	0.89	0.93	0.95	0.97	0.98	236	0.245	0.35
0.80	0.89	0.93	0.95	0.97	0.98	294	0.21	0.30
0.80	0.89	0.93	0.95	0.97	0.98	367	0.175	0.25
0.80	0.88	0.92	0.95	0.96	0.97	484	0.14	0.20

Interim analysis after 50% enrollment will be performed to assess the frequency of the primary and secondary outcomes. At that point, a decision will be made to see if there is a need to adjust the sample size.

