5. METHODS AND ASSESSMENT

5.1 Randomization and blinding

- A non-clinical research team member will create computer-generated random sequences to ensure untampered randomization. A permutated block randomization in a random fashion 1:1 ratio will be employed to prevent imbalance in groups.
- Randomization will be stratified by BMI ≥ 40 and clinic site at randomization
- Blinding: The research team collecting data will be blinded to group allocation.
 We will not be able to blind the treating physician or patient to the CGM due to the nature of the intervention.

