- Group 2 will have the device in place for a total of 7 days and reviewed by the Diabetes team after 7-10 days after CGM placement. The recommended range for glucose during pregnancy is defined as 63-140 mg/dL (18). The time above range has been defined as ≥ 140 mg/dL, greater than 10% of total CGM

placement time. Based on the results of our prospective observational study of blinded CGM placement at time of one-hour GCT of pregnant people \leq 30 weeks a CGM metric of time above range \geq 10% was associated with higher rates of adverse neonatal outcomes.

- The following criteria will currently be used to diagnose gestational diabetes in the CGM group:
 - Time above range (≥140 mg/dL) ≥ 10% of the time while using CGM or
 - Average glucose≥130 mg/dL or
 - Any glucose value ≥200 mg/dL
- Group I will receive routine prenatal care follow-up depending upon one-hour glucose results as written above.
- Group 2 will complete CGM and proceed with treatment if positive screening is found, as written above.
- Management of GDM for both groups would include:
 - Consultation and follow up with Certified Diabetes Care and Education
 Specialist (CDCES)
 - The patients will be instructed to self-monitoring of blood glucose (SMBG)
 levels four times a day through a glucometer: fasting, 1-2 hour
 postprandial as recommended by the ACOG guidelines.
 - Patients will be managed according to the ACOG recommendations of goals (2):
 - Fasting: ≤ 95 mg/dL
 - 1 hour postprandial: ≤ 140 mg/dL

- 2 hour postprandial: ≤ 120 mg/dL
- Initiation of medication if consistently elevated blood sugars following diet adjustment per provider discretion
- Participants will be asked to continue to follow up as the standard of care.
- No extra visits will be scheduled
- Both groups will be followed throughout pregnancy, delivery, and postpartum.
- A release of records form will be signed at randomization so that in case the participant delivers at another center; we can still obtain records from the delivery.
- The research team will collect participant data, including demographic characteristics, medical history, obstetric history, labor course, and maternal and neonatal outcomes, by reviewing the electronic medical records and surveying the people during prenatal visits and the 6- week postpartum clinical appointment.
- All participants will receive a \$20 gift card after completing the diabetes screening (i.e., 1hGCT/3h OGTT if screened positive/7 days with GCM).

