10. DATA HANDLING AND RECORD-KEEPING

10.1 Access to source documents

Research personnel will perform data collection through the abstraction of participant electronic medical records from multiple sites. Demographics, variables, and outcomes will be collected and entered into a Redcap database and the Dexcom data capture platform. Attached to this protocol is a detailed list of variables that will be collected. Data will be obtained from randomization up until 6 weeks postpartum.

10.2 Records Retention:

Data will be collected and de-identified in the UTHealth Redcap system. At the time of study completion, approved protocol and all other supporting documents pertaining to the project will be retained. Data will be de-identified and available for future analysis. Following completion of the study and analysis of data, the de-identified data will be shared to Dexcom Inc.

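### The primary-outcome models adjust for the randomisation strata at most, which is valid but forgoes a small precision gain from continuous BMI and, if collected, obstetric history

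*Combined protocol and SAP*

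**What the plan says.** - **Covariates.** Section 7.2 says the generalized linear models "will include stratifying variables of BMI and clinic site as covariates". It names no other baseline covariate and no sensitivity analysis with wider adjustment.
- **Form of BMI.** Section 5.1: "Randomization will be stratified by BMI ≥ 40 and clinic site at randomization". Section 7.2 does not state the coding, so the yes/no form is inferred from Section 5.1.
- **Primary model.** Section 7.2: "Primary outcome and all other binary outcomes will be analyzed with a logistic model". Results are to be given as relative risks, without saying how these come out of a logistic model.
- **Bayesian model.** Section 7.2: "The composite primary outcome will be evaluated with a Bayesian binomial model". No covariates are mentioned. The prior is set on the relative risk, centred at 1.0 with a 95% interval of 0.3–3.3. The sample size in Section 7.1 is built on this analysis.
- **Baseline data.** Section 5.4 describes the data collected as "including demographic characteristics, medical history, obstetric history, labor course, and maternal and neonatal outcomes". Section 10.1 adds: "Attached to this protocol is a detailed list of variables that will be collected". That list is not in the text available for review.

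**The concern.** BMI must be known to assign the stratum, so continuous BMI is in hand at randomisation. The plan itself treats BMI as prognostic: Section 7.1 lowers the expected event rate from 40% to 25%, partly because it expects lower BMI. A single cut at 40 ignores any gradient among participants below 40 and among those above it. Obstetric history is collected in some form but enters no primary model.

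What is at stake is precision. Prespecified adjustment for prognostic baseline variables raises power and reduces the effect of chance imbalance in those variables, with no added participants. There is also a question of consistency. If the Bayesian model omits the strata while the logistic model includes them, two analyses of one outcome can differ for reasons unrelated to the choice of framework.

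**Working it through.** **1. Reproduce the plan's figures.** Inputs from Section 7.1 and Table 4: 0.25 versus 0.175, 367 per group, 1:1. With pooled variance under the null and a one-sided test at α = 1 − threshold:

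n = [z(1−α)·√(2p̄q̄) + z(power)·√(p₁q₁ + p₂q₂)]² / (p₁ − p₂)²

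Here p̄ = 0.2125, √(2p̄q̄) = 0.5785 and √(p₁q₁ + p₂q₂) = 0.5761. At α = 0.05 and 80% power, n = (1.645 × 0.5785 + 0.842 × 0.5761)² / 0.075² ≈ 367 per group.

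| Threshold | 70% | 75% | 80% | 85% | 90% | 95% |
|---|---|---|---|---|---|---|
| Table 4 | 0.98 | 0.97 | 0.95 | 0.93 | 0.89 | 0.80 |
| Formula | 0.975 | 0.965 | 0.950 | 0.927 | 0.886 | 0.800 |
| Neutral prior, SD of log RR = ln(3.3)/1.96 = 0.609 | 0.975 | 0.965 | 0.949 | 0.924 | 0.880 | 0.786 |

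Enrolment: 734/0.90 = 815.6, so 816. The plan's figures reproduce without covariates, so its power does not rely on adjustment. Section 7.1 states a 75% threshold, while 367 per group matches 80% power at 95%, so both thresholds are reported below.

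**2. Analytic range.** If the extra covariates explain a further share R² of outcome variance, the effective sample is n/(1 − R²). The documents give no R², so these values are assumptions.

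| R² | n per group for the planned power | Power at 95% (from 0.800) | Power at 75% (from 0.965) |
|---|---|---|---|
| 0.01 | 364 | 0.804 | 0.966 |
| 0.02 | 360 | 0.807 | 0.967 |
| 0.05 | 349 | 0.818 | 0.970 |
| 0.10 | 331 | 0.836 | 0.975 |

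**3. Simulation.** All runs use 367 per group at 25% versus 17.5%. They compare the planned covariates with the same set plus continuous BMI and one binary history factor. The BMI distributions and odds ratios (OR) are assumed.

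*Set A* (1,500 trials per scenario; BMI mean 30, SD 6.7, 8% at or above 40; history prevalence 8%; OR 1.28–1.57 per 5 BMI units, history OR 2–3):
- effective-sample ratios 1.016, 1.037, 1.048
- power at 95%: 0.815→0.819, 0.810→0.817, 0.817→0.835
- power for a two-sided 95% interval: 0.724→0.729, 0.724→0.737, 0.715→0.748

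*Set B* (4,000 trials; BMI mean 30.5, about 10% at or above 40; history prevalence 10%; site not simulated):

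| OR per SD of BMI, OR history | Power at 95% | Power at 75% | Residual variance ratio | Inverse |
|---|---|---|---|---|
| 1.2, 1.5 | 0.783→0.787 | 0.961→0.960 | 0.9933 | 1.007 |
| 1.3, 2.0 | 0.797→0.800 | 0.964→0.967 | 0.9830 | 1.017 |
| 1.5, 3.0 | 0.802→0.815 | 0.968→0.971 | 0.9577 | 1.044 |
| 1.8, 4.0 | 0.805→0.835 | 0.969→0.974 | 0.9292 | 1.076 |

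*Set C* (4,000 trials; the BMI mean and SD and the end-point odds ratios of set A, plus a middle pair of 1.4 and 2.5):
- effective-sample ratios 1.016–1.058
- gain at 95%: 1.1–1.9 points
- power at 75%: 0.964→0.966, 0.966→0.970, 0.966→0.975
- stratum and site versus no covariates: worth 0.8–1.9% effective sample and less than 1 power point

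**4. Noise.** With 1,500 paired trials, the standard error of a power difference at 95% is about 0.5 points. With 4,000 it is about 0.5 × √(1500/4000) = 0.3. The smallest gains at 95% (0.4 and 0.7 points in A, 0.4 and 0.3 in B) cannot be told from zero.

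**5. Scale.** In set B at 1.5 and 3.0, the standard error of the conditional log odds ratio rises from 0.185 to 0.190 while power also rises. The precision gain shows on the marginal relative risk, so the fix must say how that is obtained.

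**6. Model size.** Expected events are 367 × 0.25 + 367 × 0.175 ≈ 156. Treatment (1), four sites (3), the stratum (1), BMI (1), history (1) and parity (1) make 8 terms, or about 19 events per term.

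**The case against.** The strongest reply is that nothing here is an error. Adjusting for the stratification factors is an accepted choice, the sample size was computed without covariates, and at the plan's stated 75% threshold the gain is at most about 1 point. All of that stands.

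Four further points also stand:

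- **Every prognostic input is assumed.** A reader might infer that the cut at 40 separates only a small minority. Section 7.1 says only that BMI should be lower than in the earlier study and gives no share at or above 40. It also counts the 734 as people diagnosed with gestational diabetes, whose BMI mix may differ from the one simulated.
- **The Bayesian gap is silence.** A reader might infer that the Bayesian model leaves out the strata. Section 7.2 opens by covering all outcomes with models that carry them, and a binomial model can be one of these. The text neither includes nor excludes covariates there.
- **Availability is unconfirmed.** Prior gestational diabetes, a prior large infant and parity are not named in Section 5.4, and the variable list is an attachment. Parity was not simulated.
- **The change takes more than a covariate list.** The prior is on the relative risk, whereas a covariate-adjusted logistic model has a conditional odds ratio as its parameter.

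The reply does not remove the case for stating the covariates. Continuous BMI is already known, and both the coding of BMI and the content of the Bayesian model are open as written.

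**Conclusion.** The point holds as an optional efficiency gain with some under-specification. It is not a flaw in validity. A reader might infer that the primary comparison is biased or underpowered for lack of covariates. The documents do not support that, because the planned power reproduces with none.

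The gain is about 1–6% effective sample (734 × 0.01 ≈ 7 to 734 × 0.06 ≈ 44 participants), with about 8% in the strongest scenario run. That corresponds to about 0–3 power points at the 95% threshold and at most about 1 at 75%. These sizes rest on assumed odds ratios, BMI distribution and history prevalence. The direction is secure if BMI or obstetric history predicts the composite; the exact size is not.

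**What to change.** In Section 7.2, before any outcome data are seen and so before the interim look at 50% enrolment, state that:

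1. The logistic and the Bayesian models for the primary outcome both include clinic site, the BMI ≥ 40 stratum and continuous BMI at randomisation. Prior gestational diabetes or a prior large infant, and parity, are added if the variable list confirms they are collected.
2. Missing covariate values are handled by one simple rule, for example single imputation from baseline data without regard to group.
3. The relative risk is obtained by standardisation over these covariates.
4. In the Bayesian model the neutral prior stays on the relative-risk scale, for example with a log-link model, or the text says how it is translated to the log odds ratio.

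The cost is a short SAP paragraph, a check of the variable list and some work on the prior. It needs no extra participants or visits, and the sample size can stay as it is.

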Costs will be assessed from the health system perspective based on the total costs for all the services provided to both the participating women and their neonates from randomization through either 6-weeks postpartum or discharge home (whichever is later). Hospital costs incurred within the Memorial Hermann Hospital System (MHHS) will be obtained from claims data and will be based on hospital-specific costs as assigned in the cost-accounting system for each of the 14 hospitals of the MHHS. Hospital costs incurred at hospitals outside of MHHS will be estimated based on mean costs of these encounters at MHHS. Costs for inpatient and outpatient services provided by the UTH physicians will be estimated based on UTH claims data and Relative Value Units (RVUs) from the Medicare Fee Schedule. The costs for the intervention group will be augmented by the acquisition costs of the Dexcom G6 Pro device, which will be based on the average wholesale price as listed in the Micromedex Redbook. All costs will be inflated to the year of analysis based on the Consumer Price Index for medical services.

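### If the gamma likelihood is carried into the Bayesian cost analysis, heavy-tailed costs make the interval for the cost ratio too narrow and the probability of reduced costs too extreme in both directions

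*Combined protocol and SAP*

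**What the plan says.** Section 7.2 gives three cost analyses.

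- **Frequentist.** "Differences in costs will be assessed using a generalized linear model (GLM"), with a log "link and gamma distribution". No rule for the dispersion, robust variance, bootstrap or alternative distribution is named.
- **Cost-effectiveness.** The ICER comes from a "joint GLM with log link for costs and probit for maternal or neonatal adverse outcomes". The plan adds: "We will induce dependency between costs and the adverse outcomes through shared random effects in the joint model".
- **Bayesian.** "We will also conduct a Bayesian analysis of the primary outcome and of costs and cost-effectiveness". For costs this paragraph gives only the prior: "This neutral prior will also be used to assess cost differences between the two treatment groups". That prior is centred at a ratio of 1.0, with a "95% credible interval of 0.3-3.3 encompassing the largest likely effect size". The cost likelihood is not restated. The outputs include the posterior probability of reduced costs and the probability of lying in the dominant quadrant.

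Section 6.2 defines cost as "total costs for all the services provided to both the participating women and their neonates", from randomization to the later of 6 weeks postpartum and discharge home. A long neonatal stay therefore counts in full. Lower dyad cost is a primary objective in section 3.2, although cost is listed among the secondary outcomes in 6.2.

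**The concern.** In a gamma model fitted by full likelihood, Bayesian or maximum likelihood, the shape is set by the gap between the log of the mean and the mean of the logs. A small group of very expensive dyads moves that gap far less than it moves the variance. Dyad cost is plausibly a mixture of many ordinary births and a minority of costly NICU stays. The fitted gamma would then imply a smaller variance for the mean cost than the data have.

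The plan reports a posterior probability, so a wrong standard error passes straight into the headline number. A chance imbalance in expensive stays could be reported as near-certain savings, or as a near-certain cost increase.

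**Working it through.** **Inputs from the documents.** Log-link gamma for costs and a neutral prior of 0.3–3.3 (section 7.2); 367 per group (section 7.1, Table 4). The plan states no cost variance, NICU rate, NICU cost or cost precision, so it has no cost figure to reproduce. All cost shapes below are assumptions.

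**Step 1: the prior.** On the log scale its SD is ln(3.3)/1.96 = 0.61. Against a standard error of 0.061, its weight is 0.061²/(0.061² + 0.61²), about 1%. It cannot correct a standard error that is too small.

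**Step 2: the formulas.** With n per arm and common shape k:
- gamma-likelihood SE of the log cost ratio = √(2/(n·k)), where k solves ln k − ψ(k) = ln(mean) − mean(ln);
- actual SE ≈ CV·√(2/n);
- SE ratio = 1/(CV·√k), which does not depend on n, so more participants do not help;
- approximate coverage = 2Φ(1.96 × SE ratio) − 1.

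If costs really are gamma, k = 1/CV² and the SE ratio is 1.

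**Step 3: plain log-normal costs, n = 367.** Here ln(mean) − mean(ln) = ½·ln(1 + CV²).

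| CV | ½·ln(1+CV²) | k | gamma SE | actual SE | SE ratio | coverage |
|---|---|---|---|---|---|---|
| 0.5 | 0.112 | 4.64 | 0.034 | 0.037 | 0.93 | 93% |
| 1.0 | 0.347 | 1.59 | 0.059 | 0.074 | 0.79 | 88% |
| 1.5 | 0.589 | 0.98 | 0.075 | 0.111 | 0.67 | 81% (82% simulated) |

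**Step 4: costs with a NICU tail.** Simulation at 367 per arm, 4,000–6,000 trials per scenario, no true difference, the plan's prior. Base cost is log-normal with mean 1 and CV 0.5; a fraction of dyads adds a log-normal NICU component.

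| NICU share | added mean | NICU CV | SE ratio | coverage | P(reduced cost) > 0.95 |
|---|---|---|---|---|---|
| 10% | 2 × base | 0.7 | 0.78 | 88% | about 10% |
| 8–12% | 2 × base | 1.0 | 0.71–0.72 | 84% | 11–12% |
| 8–12% | 4 × base | 1.5 | 0.47 | 66–67% | 21–22% |
| 5% | 9 × base | 1.5 | 0.34 | 52% | 28% |

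With an empirical-variance SE and the same prior, coverage is about 94–95% and the last column about 5–6%. The 0.95 cut is only a yardstick; the plan sets no threshold for costs.

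Check on the last row:
- mean = 1 + 0.05 × 9 = 1.45;
- variance = 0.25 + 0.05 × 81 × 3.25 − 0.45² = 13.21;
- CV = √13.21/1.45 = 2.51;
- actual SE ≈ 2.51 × √(2/367) = 0.185, against a simulated SD of 0.178 and a gamma SE of 0.061.

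A full MCMC fit with unknown shape, on 40 data sets from this case, gave posterior SDs equal to the approximation (ratio 1.00).

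**Step 5: direction.** In the same case P(reduced cost) is below 0.05 in 28% of null trials as well, and it averages about 0.50. The error is symmetric.

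**Step 6: what would be reported.** Posterior variance = 1/(1/SE² + 1/0.61²). For an observed cost ratio of 0.90 in the same case:
- gamma SE 0.061: posterior mean −0.104, SD 0.061, P = Φ(1.72) = 0.96, interval 0.80–1.01;
- typical empirical SE 0.16: posterior mean −0.099, SD 0.155, P = Φ(0.64) = 0.74, interval 0.67–1.23.

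For an observed ratio of 1.11 the two probabilities are 0.04 and 0.26.

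**The case against.** Four points on the other side carry weight.

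- **The Bayesian gamma likelihood is inferred.** The text gives only a prior for costs. That is true. But gamma is the only cost distribution named, and if another was meant, the likelihood is unspecified and still has to be written.
- **The frequentist model is not shown to be wrong.** With Pearson dispersion, coverage was 94–95%. This stands. The fault reaches the frequentist analysis only if the software estimates the scale by maximum likelihood, which the plan does not rule out.
- **The size depends on unstated costs.** This also stands. Excluding multiple gestations, major fetal anomalies and known diabetes (section 4.3) may shorten the tail, as may replacing outside-hospital costs with system means (section 6.2). With base CV 0.5 and no NICU tail, coverage is 93%.
- **The joint model may behave differently.** A maximum-likelihood fit of one version (gamma costs, probit outcome, a shared dyad-level normal random effect, no covariates or prior, 150 trials per scenario) covered 90–91% where plain gamma covered 65–82%. In a harsher case it covered 91% against 49%. Monte Carlo error is 2–3 points, and the random effect shifts the cost coefficient away from the ratio of arithmetic means.

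Two stronger readings are tempting. A reader might infer that the plan tilts results toward savings; the symmetry in steps 5 and 6 contradicts that. A reader might also infer that the dominance probability is overstated. Section 7.2 draws the ICER from the shared-random-effects model, so the plain-gamma results do not carry over to it.

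**Conclusion.** The point holds conditionally. If one estimated gamma shape is carried into the Bayesian cost analysis, or the frequentist scale is fitted by maximum likelihood, the cost-ratio interval is too narrow whenever costs are heavier-tailed than gamma. The probability of reduced costs is then overconfident both ways.

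Under the assumed shapes the loss runs from negligible (log-normal, CV 0.5) to severe (5% of dyads adding nine times the base mean). The actual size cannot be fixed from the documents. The simulations omit the BMI and clinic covariates, and any effect on the dominance probability remains open. The natural reading of the plan gives unreliable error bars in plausible settings and the remedy is cheap, so 7.2 should be changed before costs are analysed.

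**What to change.** In section 7.2:

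- (a) Keep the covariate-adjusted log-link mean model for costs, and state sandwich or bootstrap standard errors.
- (b) State the Bayesian cost likelihood. For the probability of reduced costs, combine the neutral prior (0.3–3.3) with a normal likelihood for the covariate-adjusted log ratio of arithmetic mean costs, using the standard error from (a). Alternatively, use a tail-robust cost model with a posterior predictive check of the variance.
- (c) For the dominant-quadrant probability, report a non-parametric bootstrap of dyads alongside the joint model, resampling cost and outcome together. The normal likelihood in (b) concerns cost alone and cannot supply this joint probability.

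The cost is SAP wording and a little programming, with no extra participants or data. Cost intervals will be wider.

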7. SAMPLE SIZE AND STATISTICAL METHODS

7.1 Determination of Sample Size

As stated above, based on the results of our prospective observational study of blinded CGM placement at time of one-hour GCT of pregnant people ≤ 30 weeks

#UTHealth

IRB NUMBER: HSC-MS-22-0153 IRB APPROVAL DATE: 07/05/2023 gestation we would like to adjust the sample size for this trial. A CGM metric of time above range ≥ 10% was associated with higher rates of adverse neonatal outcomes of preterm birth, intravenous glucose therapy and longer hospitalization. The findings of this study serves as the basis of diagnosis of GDM through CGM for our trial. Based on the results of this prospective trial the estimated rate of the primary outcome was 40%. In this trial we would include a more diverse population with a lower rate of factors associated with GDM such as lower BMI, different race and ethnicity. Our assumption is that the rate of the primary outcome will be 25%.

Sample size calculations using a Bayesian analysis with different probability thresholds are presented in Table 4. In order to detect a 30% reduction in the rate of adverse neonatal outcome between the control and intervention with 90% power and a Bayesian posterior probability of 75% (of any reduction), 734 individuals (367 per group) will need to be diagnosed with GDM. With a 10% loss to follow up, 816 people in total will need to be enrolled. A total of 1020 individuals would need to be approached, to accommodate an expected enrollment rate of 80%.

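### Section 7.2 does not say whether the logistic or the Bayesian analysis decides the primary outcome, and the power and threshold paired in 7.1 do not match Table 4.

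*Combined protocol and SAP*

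**What the plan says.** Section 7.2 begins with a frequentist analysis: "All outcomes will be analyzed using generalized linear models (GLMs) and will include stratifying variables of BMI and clinic site as covariates". It continues: "Primary outcome and all other binary outcomes will be analyzed with a logistic model". Relative risks with 95% confidence intervals are to be reported.

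Under the planned Bayesian analysis, the same section says "We will also conduct a Bayesian analysis of the primary outcome and of costs and cost-effectiveness" and "The composite primary outcome will be evaluated with a Bayesian binomial model". The prior is centred on a relative risk of 1.0 with a 95% credible interval of 0.3 to 3.3. The outputs are the relative risk, its credible interval and the probability of a reduction.

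The sample size in 7.1 rests only on a Bayesian criterion: a 30% reduction from a 25% control rate, "with 90% power and a Bayesian posterior probability of 75% (of any reduction"), for which 367 per group are said to be needed. Table 4 in 7.2 is titled "Bayesian power to declare efficacy depending on level of evidence (probability threshold") and gives power at six thresholds from 70% to 95%.

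**The concern.** The plan's cues about which analysis decides point in different directions. The order of 7.2, and its use of a word meaning an addition, suggest that the logistic model leads. The sizing in 7.1 and the reference to declaring efficacy in the title of Table 4 suggest that the Bayesian analysis decides. The 75% figure appears in the sizing sentence and as one of six table columns, and 7.2 never adopts it as a decision rule. No alpha is given for the logistic analysis, and no power.

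The sizing sentence does not settle the matter, because its two figures do not belong to the same column of the 367 row in Table 4. A reader cannot tell whether 75%, 90% or 95% was meant.

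Two things are at stake. A result can meet a lenient posterior rule while the confidence interval includes 1, and the plan does not say what would then be concluded. Also, 7.2 allows the sample size to be adjusted after 50% enrolment, and that decision needs a fixed power target.

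**Working it through.** **Inputs.** Control rate 0.25, treatment rate 0.175 and 367 per group (7.1 and Table 4); prior on RR with 95% interval 0.3 to 3.3 (7.2). *Assumptions:* 367 per group analysed, no covariates, and the 95% interval read as a two-sided 5% rule, since the plan states no alpha.

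**Method.** Prior SD on log RR = (ln 3.3 − ln 0.3)/(2 × 1.96) = 0.612. For x₁ control and x₂ CGM events, log RR = ln(x₂/x₁), with variance v = 1/x₁ + 1/x₂ − 2/367. The posterior mean is m = (log RR/v)/(1/v + 1/0.612²), the posterior SD is s = (1/v + 1/0.612²)^(−1/2), and Prob(RR<1) = Φ(−m/s). Power is the sum of the two binomial probabilities over all event pairs that meet the rule.

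**Step 1: reproduce the Table 4 row for 367.** In the extracted text this row runs in reverse order. Power must fall as the threshold rises, so the reading is not in doubt.

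| Threshold | 70% | 75% | 80% | 85% | 90% | 95% |
|---|---|---|---|---|---|---|
| Table 4 | 0.98 | 0.97 | 0.95 | 0.93 | 0.89 | 0.80 |
| Recomputed, stated prior | 0.975 | 0.965 | 0.949 | 0.924 | 0.880 | 0.786 |
| Recomputed, flat prior | 0.977 | 0.965 | 0.950 | 0.927 | 0.886 | 0.800 |

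The row reproduces to within two points.

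**Step 2: test the pair stated in 7.1.** The smallest number per group giving 90% power at the 75% threshold is 237 with the stated prior and 222 with a flat prior. So 367 does not follow from that pair. Ninety percent power needs about 389 to 400 per group at the 90% threshold and about 508 to 520 at 95%. The rows for 236, 294, 367 and 484 per group all show 0.80 at 95%. The usual two-proportion formula with one-sided alpha 0.05 and 80% power also gives 367. Those rows therefore look sized for 80% power at the 95% threshold, though that is an inference.

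**Step 3: power if the confidence interval decides.** With a pooled rate of 0.2125, SE₀ = √(2 × 0.2125 × 0.7875/367) = 0.0302 and SE₁ = √((0.25 × 0.75 + 0.175 × 0.825)/367) = 0.0301. Power = Φ((0.075 − 1.96 × 0.0302)/0.0301) = Φ(0.526) ≈ 0.70. Exact enumeration of the log-RR interval gives 0.698. Under this rule 80% power needs 466 per group and 90% needs 624.

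**Step 4: how often the rules disagree** (stated prior).

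| Posterior rule | Met when RR = 1 | Met but CI includes 1, RR = 0.70 | Same, RR = 0.80 | Same, RR = 1 |
|---|---|---|---|---|
| 75% | 24% | 27% | 47% | 22% |
| 90% | 9% | 18% | 26% | 7% |
| 95% | 5% | 9% | 11% | 2% |

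The largest disagreement for the 75% rule is 48%, at RR about 0.83. At a 97.5% threshold it is 0%, so the gap comes from the cut-offs and not from conflicting models.

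**Step 5: an example with 92 control events (25% of 367).**
- 84 CGM events: RR 0.91, 95% CI 0.71 to 1.18, Prob(RR<1) = 0.750, just above the cut.
- 70 CGM events: RR 0.76, 95% CI 0.578 to 1.002, Prob(RR<1) = 0.971.
- 69 CGM events: RR 0.75, upper limit 0.989, so the interval excludes 1.

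Any count from 70 to 84 therefore meets a 75% rule with an interval that includes 1.

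**The case against.** There are four fair points on the other side.

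- **Power above target.** Power of 0.97 exceeds the 0.90 that 7.1 asks for, so on the 75% rule the trial is not underpowered and a claim of at least 90% is literally true. That stands. But 7.1 presents 367 per group as the number needed, and far fewer would meet the stated pair, so the sentence still does not explain the size.
- **No pass/fail cut.** Reporting a posterior probability without a cut-off is a legitimate Bayesian choice, and 7.2 promises only to report it. The 24% figure applies only if 75% is a success rule. This is also fair, but the protocol sizes the trial on such a cut and titles its table in terms of declaring efficacy, so readers will expect a rule.
- **Lenient against strict.** The two-sided 5% reading is ours, and a 75% cut will naturally differ from a stricter one. That is correct, and it is why the deciding cut has to be named.
- **Dependence on the prior.** The recomputed figures move slightly with the prior. With a flat prior the no-effect rates are about 25%, 10% and 5%, so any figures put in the protocol should come from the final specified model.

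Both results will be reported, so nothing is hidden. The gap is in how they will be interpreted.

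**Conclusion.** The concern holds. The plan assigns two analyses to the primary outcome and names neither as decisive, with no alpha and no adopted posterior threshold. The power and threshold paired in 7.1 do not yield 367 per group and do not sit together in the Table 4 row for that size.

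Depending on which rule is meant, power at 367 per group is 0.97, 0.89, 0.80 or about 0.70. This rests on 25% and 17.5% event rates among 367 analysed per group, no covariate adjustment, a normal approximation on log RR and, for the last figure, a two-sided 5% rule. Whether those 734 are people diagnosed with GDM or everyone randomised is a separate question and is not resolved here. The matter should be corrected; it does not invalidate the design.

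**What to change.** Before any outcome data are reviewed by arm, including at the interim look, name one deciding analysis in 7.2 and label the other supportive.

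- **If the Bayesian analysis decides** (consistent with the sizing in 7.1), state one rule of the form: success is Prob(RR<1) > X%. Give its Table 4 power and its chance of being met with no effect, computed under the final prior. Table 4 uses two rates without covariates, so if the Bayesian model is to adjust for BMI stratum and clinic, state this as an added specification.
- **If the logistic model decides** (consistent with the order of 7.2), state its alpha and sidedness. For a two-sided 5% rule, give its power at 367 per group.
- **In either case**, rewrite the sizing sentence in 7.1 so that its power and threshold come from the same cell of Table 4, and use that target in any sample size adjustment.

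The cost is wording only, with no added patients if 367 per group is kept. The stated operating characteristics will look less favourable: a high no-effect success rate at 75%, or lower power at any stricter rule. Restoring 90% power under a two-sided 5% rule would take 624 − 367 = 257 more analysed per group.
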